**Secondary Analyses (week 24)**

The primary outcome and all other efficacy outcomes with week 8 and 24 assessments will be analysed using repeated measures with a random intercept per individual. Efficacy outcomes without a week 8 will be analysed using linear regression of week 24 data only. The FAS cohort will be used, with individuals with no post baseline assessment for each outcome excluded per analysis. Missing baseline covariate data are assumed to be infrequent and imputed using cohort means.

Estimates and 95% CIs will be reported per group for all assessments (restricted maximum likelihood estimates), however pairwise comparisons will only be assessed if the overall effect of Group is significant (likelihood ratio test of nested models with/without Group). Significance will be considered at  $p < 0.05$  (two-sided) with no adjustment for multiple testing and conclusions interpreted as exploratory.

Cohort: FAS

Model (wk 8):  $Y \sim \text{Visit} + \text{Group} + \text{Visit} \times \text{Group} + \text{Sex (M v F)} + \text{AUSDRISK} + Y0 + (1 | \text{ID})$

Model (no wk 8):  $Y \sim \text{Group} + \text{Sex (M v F)} + \text{AUSDRISK} + Y0$

- Y = Week 8 and 24 assessments where available per outcome (see pg 4)
- Y0 = Baseline assessment
- Visit = week 8 and 24.
- Group: CR vs IF vs SC.
- AUSDRISK and Y0 included as a continuous linear variables.

Visual inspection of residual and random effect distributions will be undertaken. If residual distributions appear not satisfactory then log transformations will be applied and if still not satisfactory GLMMs will be considered with different error distributions.

	Group p-value	Visit (wk 8)		Visit (wk 24)	
		Est [95%CI]	p-value*	Est [95%CI]	p-value*
Outcome 1 (with wk8)					
CR v SC	PP	XX [YY, ZZ]	PP	XX [YY, ZZ]	PP
IF v SC		XX [YY, ZZ]	PP	XX [YY, ZZ]	PP
IF v CR		XX [YY, ZZ]	PP	XX [YY, ZZ]	PP
Outcome 2 (no wk 8)					
CR v SC	PP			XX [YY, ZZ]	PP
IF v SC				XX [YY, ZZ]	PP
IF v CR				XX [YY, ZZ]	PP

\*Only reported if the overall Group test is significant ( $p < 0.05$ ).

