**Secondary Analyses (week 76)**

Individuals are allowed to stop the intervention after week 24, as such the mean group and individual level effects may be quite different at week 76. Consequently we analyse week 76 data separately from the earlier weeks. All efficacy outcomes (see pg 4) will be analysed using linear regression models. The FinAS cohort will be used. Missing baseline covariate data are assumed to be infrequent and imputed using cohort means.

Estimates and 95% CIs will be reported per group for all assessments (restricted maximum likelihood estimates), however pairwise comparisons will only be assessed if the overall effect of Group is significant (likelihood ratio test). Significance will be considered at  $p < 0.05$  (two-sided) with no adjustment for multiple testing and conclusions interpreted as exploratory.

Cohort: FinAS

Model:  $Y \sim \text{Group} + \text{Sex (M v F)} + \text{AUSDRISK} + Y0$

- Y = Week 76 assessment
- Y0 = Baseline assessment
- Group: CR vs IF vs SC.
- AUSDRISK and Y0 included as a continuous linear variables.

Visual inspection of residual and random effect distributions will be undertaken. If residual distributions appear not satisfactory then log transformations will be applied and if still not satisfactory GLMMs will be considered with different error distributions.

	Group p-value	Visit (wk 76)	
		Est [95%CI]	p-value*
Outcome 1			
CR v SC	PP	XX [YY, ZZ]	PP
IF v SC		XX [YY, ZZ]	PP
IF v CR		XX [YY, ZZ]	PP
Outcome 2			
CR v SC	PP	XX [YY, ZZ]	PP
IF v SC		XX [YY, ZZ]	PP
IF v CR		XX [YY, ZZ]	PP

\*Only reported if the overall Group test is significant ( $p < 0.05$ ).

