**Weekly weight assessments**

There are non-fasting weight assessments reported every 2 weeks. These data will be analysed similarly to the other secondary analyses, with however piecewise linear effects assumed for the interventions over two time periods: weeks 1-24 and 25-76. The model will include random intercepts and slopes for individuals. Again pairwise comparisons will only be assessed if the interaction tests Time1 x Group and Time2 x Group are significant (likelihood ratio test).

Models:  $Y \sim (\text{Time1} + \text{Time2}) + \text{Group} + (\text{Time1} + \text{Time2}) \times \text{Group} + \text{Sex} + \text{AUSDRISK} + Y_0 + (1 + \text{Time1} + \text{Time2} | \text{ID})$

- Time1 = Week number (1 to 76).
- Time2 = Zero for weeks 1 to 24, and week number minus 24 for weeks 25+.

Int. p-value	Group	Estimate	Coef [95%CI]	p-value*
PP	SC	Slope: wks 1-24	XX [YY, ZZ]	PP
PP	SC	Slope change: wk 25-76	XX [YY, ZZ]	PP
	CR	Slope: wk 1-24	XX [YY, ZZ]	PP
	CR	Slope change: wk 25-76	XX [YY, ZZ]	PP
	IF	Slope: wk 1-24	XX [YY, ZZ]	PP
	IF	Slope change: wk 25-76	XX [YY, ZZ]	PP
	CR v SC	Comparison: slope	XX [YY, ZZ]	PP
	CR v SC	Comparison: slope change	XX [YY, ZZ]	PP
	IF v SC	Comparison: slope	XX [YY, ZZ]	PP
	IF v SC	Comparison: slope change	XX [YY, ZZ]	PP
	IF v CR	Comparison: slope	XX [YY, ZZ]	PP
	IF v CR	Comparison: slope change	XX [YY, ZZ]	PP

\*Only reported if the respective interaction p-values for slope and slope-change are significant.

*Adverse Event Analyses*

It is assumed that the number of AEs will be low, and as such Fisher exact tests will be used to compare: CR vs IF vs SC (ie two degrees of freedom) when the number of individuals with an event is at least 4.

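### The likelihood ratio test that gates pairwise comparisons at weeks 24 and 76 runs slightly above its 5% level; an F-test from the same models would hold it

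*SAP*

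**What the plan says.** Under *Secondary Analyses (week 24)*, the SAP uses two kinds of model. Outcomes measured at weeks 8 and 24 are "analysed using repeated measures with a random intercept per individual". For the rest, "Efficacy outcomes without a week 8 will be analysed using linear regression of week 24 data only". The Group factor has three levels: "Group: CR vs IF vs SC".

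In both cases, "pairwise comparisons will only be assessed if the overall effect of Group is significant". The test of that overall effect is a "likelihood ratio test of nested models with/without Group". The threshold is a two-sided p below 0.05. The section states that there is no multiplicity adjustment and that the findings are exploratory.

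Under *Secondary Analyses (week 76)*, every efficacy outcome is analysed by linear regression, and again "pairwise comparisons will only be assessed if the overall effect of Group is significant (likelihood ratio test"). The footnotes to both results tables confirm that pairwise p-values appear only if the gate opens.

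Neither section names a reference distribution or a small-sample correction for the likelihood ratio test.

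**The concern.** In ordinary linear regression the 2-df F-test for Group comes from the same fit and is exact when errors are normal, which the model assumes. The likelihood ratio test with a chi-square reference is only a large-sample approximation, and in linear regression it errs towards rejecting. The same tendency is expected in the random-intercept model.

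The gate carries weight in this plan because it alone decides whether an outcome's pairwise p-values are reported. With three groups at a single visit, gating unadjusted pairwise tests on an overall test holds the within-outcome error rate at the level of the gate, so the gate's true level is the figure that counts. A gate that is too easy to pass lets through a few more false group differences than the stated 5% implies, always in the same direction.

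**Working it through.** **Inputs**

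- From *Study Design Change*: N = 208 (83:83:42), 25% attrition, pre-post correlation 0.4, difference 0.4 mmol/h, SD 0.8, two-sided alpha 0.04999992.
- From the model formulas: the linear regressions have 6 mean parameters (intercept, two for Group, Sex, AUSDRISK, baseline). Group takes 2 df. In the week 8/24 model, removing Group and Visit x Group takes 4 df.
- From the *Outcomes* table: 26 efficacy outcomes, of which 8 have no week 8 assessment. Linear regression therefore covers 8 outcomes at week 24 and all 26 at week 76.
- Assumed: chi-square reference; intraclass correlation 0.5 in the simulation; about 104 people at week 76 (50% of 208) as a low-retention case.

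**The plan's own figure**

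The SAP gives no operating figure for the gate beyond its nominal 5%. Its power statement can be reproduced, and this fixes the analysed sample size it has in mind. With 83 x 0.75 ≈ 62 per active arm and adjusted SD 0.8 x √(1 − 0.4²) = 0.733:

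0.4 / (0.733 x √(2/62)) = 3.04, and power = Φ(3.04 − 1.96) ≈ 85.9% (85.4% by the noncentral t).

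This agrees with the stated figure of at least 85%. Over all three arms the analysed number is 208 x 0.75 = 156.

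**Linear regressions**

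With F the usual Group statistic, LRT = n ln(1 + 2F/(n − 6)). The chi-square gate opens when LRT > 5.991, that is, when F > ((n − 6)/2)(exp(5.991/n) − 1). Under no group effect F follows F(2, n − 6), whose upper tail is (1 + 2f/(n − 6))^(−(n − 6)/2). Since exp(−5.991/2) = 0.05, the true size reduces to

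size = 0.05^((n − 6)/n),

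and the likelihood ratio p-value that matches an exact F p-value of 0.05 is 0.05^(n/(n − 6)).

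| n analysed | basis | true size | LRT p when F p = 0.05 |
|---|---|---|---|
| 208 | no attrition | 5.45% | 0.0457 |
| 156 | 25% attrition | 5.61% | 0.0444 |
| 104 | assumed for week 76 | 5.94% | 0.0416 |

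At n = 156 the two tests disagree only when the likelihood ratio p-value lies between about 0.044 and 0.05.

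**Random-intercept model, weeks 8 and 24**

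I simulated the null model with 20,000 replicates (Monte Carlo standard error 0.15 points). The 4-df likelihood ratio test compared maximum likelihood fits. The F-test used the REML fit with n − 6 denominator df, as a simple stand-in for Kenward-Roger or Satterthwaite.

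| design | 4-df LRT | REML F-test |
|---|---|---|
| 83:83:42, 25% missing week 24 | 5.5% | 5.03% |
| 62:62:32, both visits complete | 5.7% | 5.02% |

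A shorter run of 10,000 replicates gave 5.25% and 5.38% for the 4-df likelihood ratio test. That is the same direction and compatible within simulation error.

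**What this means in counts**

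If no outcome differed between groups, 26 gates at 5% would open falsely 26 x 0.05 = 1.30 times on average. At 5.61% the figure is 26 x 0.0561 = 1.46.

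**The case against.** The strongest reply is that this hardly matters. About half a percentage point is small beside 26 tests per time point that are openly unadjusted and exploratory, and the primary comparison does not pass through this gate. That is right about size, and it is why the point ranks as a refinement. It does not explain why a test that misses its own stated level should be preferred to an exact one that is standard output.

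Second, the SAP never says chi-square. In linear regression the likelihood ratio statistic is a monotone function of F, so referred to its exact distribution it *is* the F-test. This stands as a caveat: the chi-square reading is the conventional one, not a stated one.

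Third, a likelihood ratio test gives one rule across linear, mixed and generalised models, and the F-test's exactness does not carry over to the fallback GLMMs. This also stands, and the fix allows for it.

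A reader might go further and infer that the plan contradicts itself by fitting with REML and then comparing likelihoods of models with different fixed effects. The text does not show this. The REML phrase is attached to the estimates and confidence intervals, and refitting by maximum likelihood for the nested comparison is ordinary practice. What is missing is only a statement of which fits the test compares.

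A reader might also take the problem to affect every secondary analysis. It does not: the Bayesian joint analysis has no gate. The two-weekly weight model is gated on Time x Group interactions that "are significant (likelihood ratio test"), in a random-slopes model for which no size has been worked out, so nothing is claimed about it here.

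**Conclusion.** The point holds as a small, inexpensive improvement to the week 24 and week 76 secondary analyses. With a chi-square reference, the nominal 5% gate has a true size of about 5.5% to 5.6% in the linear regressions for 156 to 208 people, and about 5.9% if only about 104 remain at week 76. In the week 8/24 random-intercept model it is about 5.5% to 5.7%.

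The linear-regression figures are exact given normal errors and the stated n. The n of 156 follows from the SAP's own attrition figure. The n of 104 is an assumption, because the SAP gives no week 76 retention. The mixed-model figures depend on the assumed intraclass correlation of 0.5 and carry simulation error.

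No confirmatory conclusion is affected.

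**What to change.** - **Linear regressions** (outcomes without a week 8 assessment at week 24, and all outcomes at week 76): gate on the 2-df F-test for Group. If outcomes are log transformed, the same test applies on the log scale.
- **Random-intercept models for weeks 8 and 24:** gate on an F-test with Kenward-Roger or Satterthwaite degrees of freedom from the REML fit, naming the terms tested (on the reading used here, Group together with Visit x Group, 4 df).
- **Wherever a likelihood ratio test is kept**, for example in the fallback GLMMs: state that it compares maximum likelihood fits, not REML fits.

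The cost is a sentence or two in each of the two sections. The tests are standard software output, and neither the models nor the sample size changes. Slightly fewer gates will open: at n = 156, those with a likelihood ratio p-value between about 0.044 and 0.05 in the linear regressions.

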### **Study Design Change**

*Changes made prior to 2nd Interim Analysis – accepted by the DMC. Primary investigator (LH) was blinded to the results of interim analysis 1.*

Given the interruption due to COVID-19 it was considered ill advised to continue accrual. Regarding study design, the study team chose to consider change in glucose control as the single primary outcome and change in HbA1c as a secondary outcome, with no further interim analyses (for efficacy).

The original design had HbA1c and glucose AUC as dual primary endpoints and envisaged 3 interim analyses (at N/6, N/3 and N/2), with a multiple testing adjusted two-sided alpha=0.05 (ie two-sided alpha=0.025 for each endpoint). Assuming 25% attrition a N=260 would provide at least 80% power for the HbA1c endpoint and >90% power for the glucose AUC endpoint.

With this new design and assuming 25% attrition and a pre-post correlation of 0.4, then a sample size of N=208 (83:83:42 in the three arms) provides at least 85% power to detect a mean difference of 0.4 mmol/h (SD=0.8) in glucose AUC between the two active interventions (two-sided alpha=0.04999992).

*At the first interim analysis (N/6) negligible alpha was spent. Assuming trial could stop for a Type I error in either outcome 6.3e-07 was spent (gsDesign).*

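### HbA1c, an original dual primary endpoint, has no error-controlled test of IF v CR; a fixed-sequence step after glucose AUC would add one at no cost to the primary

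*SAP*

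**What the plan says.** SAP, Study Design Change: "The original design had HbA1c and glucose AUC as dual primary endpoints and envisaged 3 interim analyses", with the error rate split ("ie two-sided alpha=0.025 for each endpoint"). For that design the section states: "Assuming 25% attrition a N=260 would provide at least 80% power for the HbA1c endpoint". After the first interim analysis and before the second, with DMC acceptance, the team chose "change in glucose control as the single primary outcome and change in HbA1c as a secondary outcome". For the revised design, "assuming 25% attrition and a pre-post correlation of 0.4", it states that "a sample size of N=208 (83:83:42 in the three arms) provides at least 85% power" for the glucose AUC difference between the two active arms.

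SAP, Secondary Analyses (week 24): outcomes measured at weeks 8 and 24, which include HbA1c, go into a three-arm repeated-measures model in the FAS. Pairwise contrasts are examined only after a significant overall Group test. The level is two-sided 0.05, "with no adjustment for multiple testing and conclusions interpreted as exploratory". Transformation, or a different error distribution, is decided by looking at residuals.

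SAP, Bayesian Joint Secondary Analysis: HbA1c and glucose AUC are analysed together under a sceptical prior with correlation 0.7. Posterior probabilities are reported, including one for an IF v CR difference in HbA1c beyond 0.3% in either direction. No decision threshold is attached.

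No section gives a testing order after the primary comparison.

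**The concern.** The hypothesis concerns glycaemic benefit in general, and HbA1c was one of the two endpoints on which the trial was sized. Under the current text a clear week 24 HbA1c difference between IF and CR remains exploratory even if glucose AUC is significant. Neither of the two HbA1c analyses can change that: the frequentist one is unadjusted and the Bayesian one has no decision rule.

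At stake is the strength of the trial's conclusion after a positive primary result. The validity of the primary result is not in question. A hierarchical step would let the trial conclude on both original endpoints without taking anything from the first.

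**Working it through.** **Inputs (SAP, Study Design Change, unless noted).** Original design: N=260 at 2:2:1, so 104 per active arm, or 104 × 0.75 = 78 after 25% attrition; two-sided 0.025 per endpoint; HbA1c power at least 80%. Revised design: 83 per active arm, or 83 × 0.75 = 62.25, taken as 62; two-sided 0.04999992; glucose AUC difference 0.4 mmol/h, SD 0.8, pre-post correlation 0.4. Prior correlation of the two outcomes: 0.7 (Bayesian section).

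**1. The SAP's own figure.** Baseline-adjusted SD = 0.8 × √(1 − 0.4²) = 0.733. Noncentrality = 0.4 / (0.733 × √(2/62)) = 3.037. Power = Φ(3.037 − 1.960) = 85.9% (85.4% by noncentral t). This agrees with the stated 85% or more.

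**2. HbA1c effect implied by the original design.** The SAP gives no HbA1c effect or SD for its power statement, so I solve backwards, assuming that the 80% refers to IF v CR. Noncentrality at 78 per arm = z(0.9875) + z(0.80) = 2.241 + 0.842 = 3.083. The standardised effect is 3.083 × √(2/78) = 0.494.

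**3. Stand-alone HbA1c power in the revised design.** 3.083 × √(62/78) = 2.749. Power = Φ(2.749 − 1.960) = 78.5%.

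**4. Power through the sequence.** This is the bivariate normal probability that both tests reject, with marginal powers 85.9% and 78.5%. The correlation of the test statistics is not stated, so a range is shown:

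| Correlation | Both significant |
|---|---|
| 0 | 67.5% |
| 0.3 | 69.7% |
| 0.5 | 71.5% |
| 0.7 | 73.7% |
| 0.9 | 76.7% |

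The 80% is a lower bound. Had the original HbA1c power been 85% or 90%, stand-alone power would be 83% or 88%, and sequence power at correlation 0.7 would be 77% or 81%.

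**5. Error rate.** If there is no true glucose difference, any false claim in the sequence first requires a false glucose rejection, which has probability at most 0.04999992. If there is a true glucose difference, only HbA1c can be falsely rejected, at the same level. Family-wise error is therefore held at the primary level and the primary test is unchanged.

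**6. Effect of the three-arm Group gate.** I simulated 62:62:31 completers with the standardised effect 0.494 between IF and CR, a 2-df overall test with known variance, and then the pairwise test. Both tests are significant in 67.6% of runs if the SC mean lies midway between CR and IF, 72.0% if SC equals CR, 77.2% if SC is half the effect worse than CR, and 78.3% if it is the full effect worse. The direct contrast alone gives about 78%. The gate can therefore cost up to about 11 percentage points, and a fixed sequence does not need it.

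**The case against.** The strongest reply is that nothing here is wrong. One primary outcome with exploratory secondaries is a legitimate plan, the change was made openly with DMC acceptance, and the relevant sections agree with each other. That stands. A reader might infer that the unadjusted secondary tests inflate type I error. They would if HbA1c were read as confirmatory: two tests at 0.05 give about 10% at correlation 0 and about 8% at 0.7. The SAP makes no such claim.

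A reader might also infer that the redesign gave up HbA1c with no gain to glucose AUC. That is true only in comparison with a fixed sequence. Against the original split, moving glucose from 0.025 to about 0.05 raises its power at 62 per arm from Φ(3.037 − 2.241), about 79%, to about 86%.

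Nor is HbA1c simply one of many outcomes, since the joint Bayesian analysis gives it a standing shared only with glucose AUC. That analysis controls no error rate, so it does not fill the gap.

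Finally, a reader might take 78% as the power of the proposed procedure. It is the stand-alone figure; the gate on glucose lowers it to the range tabulated above. The HbA1c effect is back-solved, and the SAP does not name the contrast behind its 80%. These are assumptions, and they limit the precision of the power figures but do not touch the error-rate argument.

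**Conclusion.** The point holds as a worthwhile, low-cost improvement and not as an error. As written, the trial cannot make a confirmatory HbA1c claim for IF v CR, whatever the data show. A fixed sequence would give a roughly 67-77% chance of one under the planning assumptions, about 74% if the SAP's prior correlation of 0.7 is used for the test statistics. The primary analysis would keep its full alpha and its power of about 86%.

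The size rests on three assumptions: that the original HbA1c power statement refers to IF v CR, that 80% is its floor, and that attrition is 25% in each active arm. That the step costs no alpha rests on none of them.

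**What to change.** Before unblinding, name HbA1c IF v CR at week 24 as the single key secondary outcome, to be tested at two-sided 0.04999992 only if the primary glucose AUC test is significant. Specify the direct week 24 IF v CR contrast from the existing repeated-measures model in the FAS, exempt it from the overall Group test, and fix the HbA1c scale in advance so that residual inspection can lead only to a sensitivity analysis. Keep all other outcomes, visits and contrasts exploratory, and leave the Bayesian analysis as it is.

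The cost is a short paragraph in the SAP and the loss of freedom to choose the HbA1c model or scale after seeing the data. No alpha, participants or extra measurements are needed. If glucose AUC is not significant, HbA1c remains exploratory, as now.

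### The week 8/24 secondary model gives visit-specific contrasts but one shared baseline slope; adding Visit x Y0 is a cheap gain in precision if the slopes differ

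*SAP*

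**What the plan says.** The SAP section Secondary Analyses (week 24) sends outcomes down one of two routes.

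- **With week 8:** "all other efficacy outcomes with week 8 and 24 assessments will be analysed using repeated measures with a random intercept per individual". The formula has main effects for visit, group, sex, AUSDRISK and Y0, a visit-by-group interaction and a random intercept. Its tail, in typeset source, is "AUSDRISK} + Y0 + (1 | \text{ID". Visit is defined by "Visit = week 8 and 24", and the covariates by "AUSDRISK and Y0 included as a continuous linear variables". Y0 appears once and is not crossed with visit.
- **Without week 8:** "Efficacy outcomes without a week 8 will be analysed using linear regression of week 24 data only".

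The results table for the first route reports pairwise group contrasts separately at week 8 and week 24. These analyses carry "no adjustment for multiple testing and conclusions interpreted as exploratory".

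The table under Outcomes marks 18 efficacy measures at both week 8 and week 24: six diet and behaviour measures, body weight, HbA1c, four fasting measures, two blood pressures, three lipid measures and hsCRP. Postprandial glucose AUC, the final primary outcome, has no week 8 assessment. It is therefore analysed by single-visit regression, both in Primary Outcome Comparison and here.

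**The concern.** The model lets the group effect vary by visit so that each visit has its own contrast, but adjusts both contrasts with the same baseline coefficient. If baseline predicts the two visits with different slopes, the shared coefficient suits neither. The random intercept cannot repair this, because it is constant over visits while a visit-dependent baseline effect is not.

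Two things would be at stake, both for the visit-specific contrasts of secondary outcomes such as HbA1c, which the design change moved from dual primary to secondary:

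- some removable baseline variation stays in the contrast;
- a chance baseline difference between arms is corrected by the wrong amount at each visit.

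**Working it through.** **Inputs from the SAP (Study Design Change).** N=208 as 83:83:42, 25% attrition, pre-post correlation 0.4, difference 0.4 mmol/h, SD 0.8, two-sided alpha 0.04999992.

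**Inputs the SAP does not give.** The baseline slopes at weeks 8 and 24 (b8, b24) for any affected outcome. They are assumed below on a standardised scale with equal SDs. The SAP's only correlation, 0.4, is for glucose AUC and is borrowed for some scenarios.

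**1. The plan's own figure.** Per active arm, 83 x 0.75 = 62.25, taken as 62. The baseline-adjusted SD is 0.8 x sqrt(1 - 0.4²) = 0.733. Power is 85.9%, which agrees with the stated minimum of 85%. Unadjusted (SD 0.8) it would be 79.5%, and with change scores 71.9%. The power claim therefore rests on baseline adjustment.

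**2. What the shared slope estimates.** With complete data and a random intercept, Y0 varies only between individuals, so its coefficient comes from each person's mean over the two visits: c = (b8 + b24)/2.

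**3. Precision.** At visit k the residual variance is 1 - bk² with its own slope, and 1 - bk² + (bk - c)² with the shared slope. The relative increase is (bk - c)²/(1 - bk²). For slopes 0.8/0.6, c = 0.7, giving 0.01/0.64 = 1.6% at week 24 and 0.01/0.36 = 2.8% at week 8.

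| b8 / b24 (assumed) | Gap | Week 24 | Week 8 |
|---|---|---|---|
| 0.4 / 0.4 | 0 | 0% | 0% |
| 0.98 / 0.93 | 0.05 | 0.5% | 1.6% |
| 0.5 / 0.4 | 0.1 | 0.3% | 0.3% |
| 0.8 / 0.7 | 0.1 | 0.5% | 0.7% |
| 0.6 / 0.4 | 0.2 | 1.2% | 1.6% |
| 0.8 / 0.6 | 0.2 | 1.6% | 2.8% |
| 0.9 / 0.7 | 0.2 | 2.0% | 5.3% |
| 0.7 / 0.4 | 0.3 | 2.7% | 4.4% |
| 0.9 / 0.6 | 0.3 | 3.5% | 11.8% |
| 0.8 / 0.4 | 0.4 | 4.8% | 11.1% |
| 0.85 / 0.45 | 0.4 | 5.0% | 14.4% |

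For a 0.5 SD effect with 62 per arm and b24 = 0.4, week 24 power is 85.9% with the term. Without it, power is 85.5% (0.6/0.4) or 84.3% (0.8/0.4). This is illustrative only, since glucose AUC itself has no week 8 visit.

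**4. Chance imbalance.** The error in the contrast at visit k is (bk - c) x imbalance: half the slope gap times the imbalance, with opposite signs at the two visits, cancelling in their average. For a 0.25 SD imbalance at week 24:

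- gap 0.2: 0.1 x 0.25 = 0.025 SD. With slopes 0.8/0.6 the SE is sqrt(0.64 x 2/62) = 0.144, so this is 0.17 SE.
- gap 0.4: 0.2 x 0.25 = 0.05 SD. With slopes 0.85/0.45 the SE is sqrt(0.7975 x 2/62) = 0.160, so this is 0.31 SE.

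The SE of the IF v CR baseline difference is sqrt(2/62) = 0.18 SD, so 0.25 SD is 1.39 SE, exceeded by chance in about 16% of outcomes. Against standard care, with 32 retained, the figure is about 25%.

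**5. Simulation.** 20,000 trials per scenario, arms 62/62/32, complete data, no true effect, week 24 IF v CR. Each pair shows the model without / with Visit x Y0.

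| b8 / b24 | Error per unit imbalance | Variance ratio (without to with) | Type I error |
|---|---|---|---|
| 0.6 / 0.4 | -0.097 / 0.004 | 1.01 | 6.7% / 6.6% |
| 0.8 / 0.4 | -0.193 / 0.007 | 1.04 | 9.5% / 9.9% |
| 0.8 / 0.6 | -0.094 / 0.006 | 1.01 | 8.5% / 8.6% |

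The mean error over randomisations was about 0 in every case. Rejection above 5% occurs equally with and without the term. It comes from assuming equal residual variance at the two visits, a separate matter that Visit x Y0 neither causes nor cures.

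**The case against.** The strongest reply is that this is a preference and not a defect. The SAP states its model fully, and a common baseline slope is an accepted simplification. Randomisation keeps the contrasts unbiased with complete data. The single-visit models elsewhere fit their own slopes only because each contains one visit, so the SAP does not contradict itself. All of this stands.

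The harm is also conditional. A reader might infer that the shared slope is too flat at week 8 and too steep at week 24, because baseline usually predicts a near visit better. The SAP gives no slope or correlation that shows this. A slope is a correlation times an SD ratio, so a larger SD at week 24 could bring the two slopes together even if correlations decay. The largest losses belong to week 8, whereas the primary comparison is set at week 24. There, even a 5.0% variance increase is only about 2.5% of the standard error.

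A reader might also infer bias or inflated type I error. With complete data the checks show neither arising from the omission. One qualification concerns dropout, since the SAP assumes 25% attrition and its full analysis set keeps people seen only at week 8. If dropout depended on baseline in one arm only, the error would no longer average to zero. A large-sample check assumed about a quarter missing at week 24, log-odds of dropout of 0.5 to 1.0 per SD of baseline in one arm, residual correlation 0.5 and slope gaps of 0.2 to 0.4. It gave a week 24 bias of about 0.02 to 0.07 SD, and about zero with the extra term. Nothing in the SAP says that such dropout will occur.

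**Conclusion.** The point holds as an optional refinement. The week 8/24 model imposes one Y0 slope on contrasts reported by visit. If the slopes are equal, nothing is lost. If they differ by 0.1 to 0.2, the week 24 contrast loses about 0.3 to 2% of its precision and the week 8 contrast up to about 5%. Gaps of 0.3 to 0.4 raise this to about 2.7 to 5% and 4.4 to 14%. The imbalance error is conditional on the realised baseline difference and has mean zero with complete data. These sizes rest on assumed slopes, equal SDs and complete data.

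The scope is the 18 exploratory outcomes with a week 8 visit. The documents do not support extending it to the primary result: the primary test, outcomes without week 8 and the week 76 analyses are all single-visit regressions and are unaffected. Nor do they support calling the present model invalid.

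**What to change.** In Secondary Analyses (week 24), add a Visit x Y0 interaction to the formula for outcomes with a week 8 assessment, and state in the bullet beneath that Y0 has a separate linear slope at each visit. Leave the formula without week 8 and the week 76 formula unchanged.

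The cost is one model term and one degree of freedom per outcome. If the slopes turn out equal, the loss is negligible: in the 0.4/0.4 simulation the standard deviation of the estimate was 0.1650 with the term and 0.1649 without. Make the change before the week 24 data are analysed, so that the term is not chosen after seeing results.
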